## **8.2 Serious adverse event reporting**

To ensure patient safety, every SAE, regardless of suspected causality, occurring after the patient begins taking study drug and until 30 days after the patient has stopped study participation must be reported to relevant regulatory authorities and IRB within 24 hours of learning of its occurrence. Recurrent episodes, complications, or progression of the initial SAE must be reported as follow-up to the original episode, regardless of when the event occurs. This report must be submitted within 24 hours of the investigator receiving the follow-up information. An SAE that is considered completely unrelated to a previously reported one should be reported separately as a new event.

The investigator must assess the relationship to study drug, complete and submit the SAE report forms. The original copy of the SAE reports and submission confirmation must be kept with the case report form documentation at the study site.

Follow-up information is sent to the same person to whom the original SAE Report Form was sent, using a new SAE Report Form stating that this is a follow-up to the previously reported SAE and giving the date of the original report. The follow-up information should describe whether the event has resolved or continues, if and how it was treated, whether the blind was broken or not, and whether the patient continued or withdrew from study participation.

### **8.3 Pregnancies**

To ensure patient safety, each pregnancy in a patient on study drug must be reported to relevant regulatory authorities and drug manufacturers within 7 days of learning of its occurrence. The pregnancy should be followed up to determine outcome, including spontaneous or voluntary termination, details of the birth, and the presence or absence of any birth defects, congenital abnormalities, or maternal and/or newborn complications. Any SAE experienced during pregnancy must be reported on the SAE Report Form.

### **8.4 Data Monitoring Committee**

A data monitoring committee (DMC) will be instituted to review safety and efficacy. The DMC will be comprised of at least 2 physicians, a pharmacist and a statistician not affiliated with the study. They will be selected based on their scientific and clinical background and have expertise in kidney transplantation.

The DMC will meet to review the available safety data after 12, 24, 36 and 48 patients enrollment to the study. Following the completion of the enrollment, the DMC will meet bi-annually and/or at the request of PI. The DMC will review the clinical and laboratory safety data and make recommendations regarding the further conduct of the study with respect to safety. If a safety concern is identified, the DMC will determine whether or not dosing should be continued or modified depending on the event and occurrence of other adverse events.

Decisions based on the recommendations of the Board will take into account the potential risks and benefits associated with continuing enrollment of patients in the study. The final decision with respect to the modification of the protocol will be made by the PI after having discussion with a selected group of experts. In the event of study termination, all health authorities, IRB and DMC would be notified of the termination within one business day.

## **9 Data review and database management**

### **9.1 Data collection**

The study staff will enter the study-related patient data required by the protocol into the study-specific electronic Case Report Forms (CRFs) that conforms to 21 CFR 312.62 requirements. Once the content of the electronic CRFs are reviewed for accuracy against the patient record, the data will be entered into a Georgetown University hosted HIPAA compliant electronic Web-based database (REDCap).

## **9.2 Database management and quality control**

A designated study staff member will act as a data manager, will check for data discrepancies and, by generating appropriate queries, allow the data to be confirmed or corrected. The Investigator must certify that the data entered into the CRFs are complete and accurate.

Concomitant medications entered into the database will be coded using the WHO Drug Reference List, which employs the Anatomical Therapeutic Chemical classification system. Medical history/current medical conditions and adverse events will be coded using the Medical dictionary for regulatory activities (MedDRA) terminology.

Laboratory samples will be processed at the hospital affiliated laboratory and the results will be available via the hospital and clinic information systems electronically.

At the conclusion of the study, unused study drugs will be returned to Novartis and the occurrence of any protocol deviations will be determined. After these actions have been completed and the database has been declared to be complete and accurate, it will be locked and made available for data analysis (Section 10). Any changes to the database after that time can only be made by joint written agreement between the investigator and a contracted statistician.

## **10 Data analysis**

A contracted statistician at the Georgetown-Howard Center for Clinical and Translational Research will perform the statistical analysis.

### **10.1 Populations for analysis**

Full Analysis Set (FAS; intent-to-treat) consists of all randomized patients who received at least one dose of study drug. Following the intent-to-treat principle, patients will be analyzed according to the treatment they were assigned to at randomization.

Safety Set (SS) consists of all patients who received at least one dose of study drug and had at least one post-baseline safety assessment. Patients will be analyzed according to treatment received. Of note, the statement that a patient had no adverse events also constitutes a safety assessment.

Per Protocol Set (PPS) consists of all FAS patients without a major protocol violation and/or deviation, and who have completed the study. Analysis will be conducted in this set as well.

Efficacy analysis will be performed on the FAS, as defined above, with patient data analyzed according to the treatment groups to which they were randomized. It will also be done on the SS and PPS with patient assignment as treatment actually received.

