## **6.4 Treatment Blinding**

This is an open-label study. Therefore, after randomization, the investigator, pharmacist and patient will be aware of which treatment is administered to the patient. The investigator should, however, withhold the treatment assignment from the local pathologist interpreting the biopsies. The local pathologist will provide the investigator their interpretation for clinical management of the patient.

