#### **6.5.7.2 Initiation and maintenance of Tacrolimus**

It is recommended that the initial dose of TAC be administered according to our standard of care practice within 24 hours after reperfusion of the graft. If patients experience DGF, TAC can be held for up to and including 14 days. However, TAC or study medication (ERL or MMF/MPA) must be started within 24 hours post-transplant. Subsequently, ERL dosing will be adjusted according to trough level results from the reference laboratory. Tacrolimus whole-blood trough concentrations will be determined on all study visits. Target TAC trough levels will be as follows in Table 6-1. Target therapeutic ranges for TAC C0-h levels in whole blood will be assessed at the hospital laboratory for purposes of this protocol.

If, for any time throughout the study, TAC is held for > 14 days, ERL should be discontinued and the patient discontinued from the study. These patients should be followed throughout the remainder of the study to Month 24 on a follow-up schedule. See Section 7.5, Safety assessments, Follow-up of prematurely discontinued patients.

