#### **10.4.2 Statistical model, and method of analysis**

The primary analysis will be the comparison of ERL with TAC based on FAS using an analysis of variance (ANOVA) model. Stratification factors applied at randomization will be included as binary factors in the ANOVA model in addition to treatment group.

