#### **10.7 Power for analysis of critical secondary variables**

Correlation between laboratories will be checked periodically throughout the study period. eGFR will be calculated using MDRD formula for each visit following the kidney transplantation. All data will be analyzed using the intent-to-treat approach as well as on-treatment based approach. Comparisons between treatment groups experiencing composite efficacy failure and each component will be analyzed with Fisher's exact test. The Chi-square and/or one-way analysis of variance (ANOVA) will be used for acute rejection episodes and creatinine levels respectively.

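### The set labelled intent-to-treat leaves out randomized patients who never took study drug, and no other analysis set includes them, in an open-label trial where the arm is known before dispensing

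*Combined protocol and SAP*

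**What the plan says.** Section 10.1 defines three analysis sets, and each depends on dosing.

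- FAS: "Full Analysis Set (FAS; intent-to-treat) consists of all randomized patients who received at least one dose of study drug". Within it, "Following the intent-to-treat principle, patients will be analyzed according to the treatment they were assigned to at randomization".
- Safety Set: "Safety Set (SS) consists of all patients who received at least one dose of study drug and had at least one post-baseline safety assessment".
- Per Protocol Set: "Per Protocol Set (PPS) consists of all FAS patients without a major protocol violation and/or deviation, and who have completed the study". As a subset of the FAS, it inherits the dose requirement.

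Section 10.4.2 says "The primary analysis will be the comparison of ERL with TAC based on FAS", and Section 10.5.1 puts the secondary efficacy variables on the FAS as well. The synopsis and Section 10.7 promise: "All data will be analyzed using the intent-to-treat approach as well as on-treatment based approach". Neither gives another definition of intent-to-treat.

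On who knows the arm, Section 6.4 says "after randomization, the investigator, pharmacist and patient will be aware of which treatment is administered to the patient". Only the local pathologist is to be kept unaware. Under Section 6.3 the investigator or coordinator randomizes from envelopes, then tells the Research Pharmacy the arm, and only then is drug dispensed.

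On timing, Sections 4 and 6.2 place randomization within 24 hours of transplantation, and Section 4 places the first dose of study drug in the same window. Table 7-1 marks randomization in the screening column (day -21 to 0).

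**The concern.** Intent-to-treat protects the comparison because membership of the set is fixed at randomization, before anything the arm can influence. Here membership is fixed at the first dose, after the people deciding on that dose have learned the arm. If the reasons for not starting differ between everolimus and MMF/MPA, the patients who remain are no longer randomized groups.

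The patients left out would matter to the endpoint. With randomization within 24 hours of transplantation, a non-starter is a transplant recipient who can still reject, lose the graft, die or be lost to follow-up, and these are the components of the primary composite. No planned sensitivity analysis brings such a patient back. The design is described as non-inferiority, with no margin stated, so a shift in either direction in a small arm could change how the pilot result is read.

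**Working it through.** **Inputs from the documents.** Sections 6.3 and 10.6: 16 patients per arm. Section 10.6: a pilot rule of 12 per group, 20% dropout, block size 12, allocation 1:1:1.

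**The plan's own figure.** 12 / (1 - 0.20) = 15 per arm. A block of 12 at 1:1:1 holds 4 patients per arm, so 15 rounds up to 4 blocks: 4 x 4 = 16 per arm and 48 in total. The stated number reproduces, and it counts randomized patients.

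**Does any set hold all randomized patients?** The FAS needs a dose. The Safety Set needs a dose and a later assessment. The Per Protocol Set lies inside the FAS. The answer is no.

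**Is the arm known before the first dose?** The order in Section 6.3 is envelope, notice of the arm to the pharmacy, dispensing. The answer is yes for those who decide whether drug is given.

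**Size.** One patient is 1/16 = 6.25% of an arm. Let e be the failures among all 16 randomized to an arm, k the non-starters, and f the non-starters who failed. Then

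shift = (e - f)/(16 - k) - e/16.

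The shift is negative when f/k exceeds e/16, positive when f/k is below e/16, and zero when they are equal or k = 0.

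The documents give neither a failure rate nor a non-starter rate. Assume e = 4, that is 4/16 = 25.0%:

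| Non-starters k | All failed (f = k) | Shift, points | None failed (f = 0) | Shift, points |
|---|---|---|---|---|
| 0 | 4/16 = 25.0% | 0 | 4/16 = 25.0% | 0 |
| 1 | 3/15 = 20.0% | -5.0 | 4/15 = 26.7% | +1.7 |
| 2 | 2/14 = 14.3% | -10.7 | 4/14 = 28.6% | +3.6 |
| 3 | 1/13 = 7.7% | -17.3 | 4/13 = 30.8% | +5.8 |

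**Range over the assumed rate.** For one to three non-starters:

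- 3/16 failures: -5.4 to -18.8 points if all failed; +1.3 to +4.3 if none did.
- 6/16 failures: -4.2 to -14.4 points if all failed; +2.5 to +8.7 if none did.

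**Effect on a test.** Against a control arm at 4/16, the all-failed rows for k = 1, 2 and 3 give Fisher p-values of 1.00, 0.66 and 0.34. In these cases the rule moves the estimate without producing a significant result.

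**The case against.** The strongest reply is that the rule will rarely apply. As planned, randomization and first dose fall within hours of each other. One later dose is enough to enter the FAS, dosed patients are analysed as assigned, and the dose condition stands openly beside the label. All of this stands, and with no non-starters the two definitions give identical results. One qualification is that Table 7-1's placement of randomization conflicts with Sections 4 and 6.2 and, if followed, would lengthen the gap before the first dose.

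A reader might also infer more than the documents support:

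- **That the plan lets patients with poor early graft function go without everolimus.** Section 6.5.7.2 says "However, TAC or study medication (ERL or MMF/MPA) must be started within 24 hours post-transplant". This follows directly on permission to hold tacrolimus in delayed graft function. In that setting it requires study medication within 24 hours, which works against non-starting. If tacrolimus is started, the wording at most leaves room for delay.
- **That wound-healing concerns would keep everolimus from being started.** The provision in Section 4 covers patients in Arms 1 and 2 who are having severe side effects and allows everolimus to be held. Those patients have been dosed and are in the FAS.
- **That the rule flatters everolimus.** The sign depends on whether the excluded patients fail more or less often than the rest of their arm, and the documents say nothing about that.
- **That everyone knows the arm.** The local pathologist should not, though the pathologist has no part in starting drug.
- **That never-dosed patients would have no outcome data.** Section 7.1 limits data collection for screening failures, whom it defines as leaving before randomization. The real gap is narrower: Table 7-1 times the follow-up record from the first dose.

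**Conclusion.** The point holds as a defect of definition with a possible effect. It is not evidence of selective removal. The set called intent-to-treat is not all randomized patients, no set is, and the main efficacy analyses rest on it. Open-label dispensing means that exclusion could depend on the arm, and the resulting bias could go either way.

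The likely number of non-starters is small and may be zero. At 16 per arm even one counts for 6.25% of an arm. Under an assumed 4/16 failure rate, one to three non-starters shift an arm's rate by -5.0 to -17.3 points if all failed and by +1.7 to +5.8 points if none did. These figures illustrate sensitivity and do not forecast bias, because both the failure rate and the number of non-starters are assumed. The change is worth making because it removes the question at little cost.

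**What to change.** 1. In Section 10.1, define the FAS as all randomized patients, analysed as randomized whether or not they were dosed. Keep the at-least-one-dose rule for the Safety Set.
2. If the present set is wanted, rename it modified intent-to-treat and use it as a sensitivity analysis. State there whether tacrolimus counts as study drug; Sections 6.5.5 and 6.5.8 use the term for everolimus or MMF/MPA.
3. Apply the existing off-drug follow-up to never-dosed patients, timed from randomization or transplantation. The synopsis already counts from randomization, and Section 6.5.8 and the follow-up text after Section 7.5.11 count from transplantation. The follow-up row of Table 7-1 needs amending because it counts from the first dose.
4. Reconcile the randomization entry in Table 7-1 with Sections 4 and 6.2.
5. Report non-starters by arm, with reasons.

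The cost is a few edits to Section 10.1 and Table 7-1, and follow-up of probably few never-dosed patients through existing visits. The sample size stays at 48.

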## **10.2 Patient demographics/other baseline characteristics**

Demographic and other baseline characteristics will be recapitulated by treatment group. Unless otherwise specified, continuous variables will be summarized with the number of non-missing observations, mean, median, standard deviation, minimum and maximum. Discrete and categorical variables will be summarized by frequencies and percentages.

## **10.3 Treatments (study drug, rescue medication, other concomitant therapies, compliance)**

The average daily dose of ERL, MMF/MPA, and TAC will be recapitulated within the defined period by treatment group.

On calculating dosage averages over a time period, zero doses will be used for periods of study medication interruption regardless of the reason (i.e. suspected drug toxicity, adverse events, non-compliance, etc).

The reasons for ERL, MMF/MPA, or TAC dose adjustment will be assessed at certain periods and summarized by treatment group.

The duration of exposure for ERL, MMF/MPA and TAC, measured in days since the first administration of the study medication, will be summarized. Note that duration of exposure includes periods of temporary interruption of respective medication.

Summary statistics will be presented for total daily dose of corticosteroids, expressed in doses equivalent to prednisone. These calculations will include any steroids used for the treatment of rejection episodes.

Other immunosuppressive therapies will be summarized by WHO drug names by treatment group. The tables will show the number of patients receiving these drugs at any time, and percentages.

All non-immunosuppressive medications or non-drug therapies will be grouped into prior and concomitant medications and summarized separately by treatment group.

All of the analysis will be performed on the SS.

## **10.4 Analysis of the primary objective(s)**

Patients' data will be summarized with respect to demography and baseline characteristics, including information on donor and recipient and on transplant procedures, for SS as 1 group, for FAS and PPS by the randomized treatment groups.

Efficacy will be analyzed on the pooled SS, and on FAS and PPS comparing the 3 treatment groups. Efficacy variables include BPAR, graft loss, death and combinations thereof.

Safety and tolerability will be assessed in terms of treatment-emergent adverse events, laboratory tests and vital signs measurements. Safety analyses will be conducted on the SS, and on FAS comparing the 3 treatment groups.

#### **10.4.1 Variable**

The primary efficacy variable is the composite efficacy failure rate (treated BPAR, graft loss, death or loss to follow-up) at 6, 12 and 24 months post-transplant. The secondary variable is renal function assessed as eGFR during the first 24 months post-transplantation, determined by the MDRD formula. Other secondary variables include the incidences of CMV and BKV, new onset diabetes mellitus, chronic kidney disease with associated proteinuria, adverse events, serious adverse events and tacrolimus associated adverse events.

#### **10.4.2 Statistical model, and method of analysis**

The primary analysis will be the comparison of ERL with TAC based on FAS using an analysis of variance (ANOVA) model. Stratification factors applied at randomization will be included as binary factors in the ANOVA model in addition to treatment group.

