### **Statistical analysis:**

All data will be analyzed using the intent-to-treat approach as well as on-treatment based approach. Comparisons between treatment groups experiencing composite efficacy failure and each component will be analyzed with Fisher's exact test. The Chi-square and/or one-way analysis of variance (ANOVA) will be used for acute rejection episodes and creatinine levels respectively.

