### **Sample size justification:**

Since this is a pilot study, the sample size estimation method proposed by Julious was considered in order to minimize the sample size (14). Julious proposes to employ sample size of 12 per group for a pilot study (14). Assuming the drop out rate of 20% along with the ease of blocked randomization, we propose the sample size of 16 per arm, totaling 48 patients. The estimated effect size,  $\alpha$ , and  $\beta$  corresponding to this sample size are 0.9, 0.05 (two-sided), and 0.2 respectively (15). A block size of 12 along with an allocation ratio of 1:1:1 will be employed as a randomization scheme.

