### 6.2 Treatment Arms

Within 24 hours after transplantation, after having met all inclusion/exclusion criteria, patients will be randomized to one of the following treatment groups in a ratio of 1:1:1. All patients will receive Campath or Simulect as induction therapy as well as Solumedrol infusion.

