### 6.3 Treatment Assignment

Once a potential study patient is identified and he/she fulfills the inclusion/exclusion criteria and the informed consent form is signed, the patient will be entered into the study.

The patient will be assigned a patient identification number sequentially ( 001, 002 etc) Randomization will be performed by the Principal Investigator and/or the clinical research

coordinator using randomization envelopes which each have been randomly assigned a treatment group. A total of 16 patients will be randomized into each treatment group.

If a patient fulfills the conditions to be randomized, the study team will notify Research Pharmacy staff with the treatment arm and a subject ID number. The Research Pharmacy will then dispense the assigned drug accordingly.

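### Section 10.4.2 sets a primary analysis that cannot be run as written and conflicts with the Fisher's exact test assigned to the same composite; contrast, time point and components also differ between sections

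*Combined protocol and SAP*

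**What the plan says.** **Primary analysis (10.4.2).** "The primary analysis will be the comparison of ERL with TAC based on FAS using an analysis of variance (ANOVA) model". The next sentence adds: "Stratification factors applied at randomization will be included as binary factors in the ANOVA model". No outcome or time point is given.

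**Primary variable (10.4.1).** "the composite efficacy failure rate (treated BPAR, graft loss, death or loss to follow-up) at 6, 12 and 24 months post-transplant". This is a yes/no outcome for each patient.

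**Test named elsewhere.** The synopsis (Statistical analysis) and section 10.7 carry the same sentence: "Comparisons between treatment groups experiencing composite efficacy failure and each component will be analyzed with" Fisher's exact test. Both then add: "The Chi-square and/or one-way analysis of variance (ANOVA) will be used for acute rejection episodes and creatinine levels respectively".

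**Randomization.** Sections 6.2 and 6.3 give "patients will be randomized to one of the following treatment groups in a ratio of 1:1:1" and "A total of 16 patients will be randomized into each treatment group", using envelopes. The synopsis and 10.6 add: "A block size of 12 along with an allocation ratio of 1:1:1 will be employed as a randomization scheme". None of these places names a stratification factor. Induction therapy is a stratum or main effect in 10.4.4, 10.5.1 and 10.5.2, but no section says that randomization used it.

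**Contrast.** The synopsis objectives and the objectives under section 1 compare the everolimus arms with the MMF/MPA arm. Section 3.1 compares everolimus plus low-dose tacrolimus with MMF/MPA, which reads as Arm 1 vs Arm 3. Section 10.4 compares three groups. The Kaplan-Meier paragraph of 10.4.4 compares two.

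**Time point.** Month 24 in the objectives under section 1 and in 3.1. Months 6, 12 and 24 in the synopsis objectives, section 4 and 10.4.1.

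**Components.** Delayed graft function is in the composite in the synopsis objectives and under section 1. It is absent from the synopsis efficacy assessments, 3.1, 10.4.1 and 10.4.4.

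**The concern.** A statistician given only 10.4.2 could not run the primary analysis. The model needs strata that are not named. The contrast is unclear on either reading. If tacrolimus is the comparator, no such arm exists, because all arms start on it (6.1, 6.2). If the phrase means the everolimus-plus-tacrolimus regimen, its comparator is missing.

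Two tests are also in play for one endpoint. If 10.4.2 was meant for a continuous outcome instead, then the section on the primary objective names no primary test for the composite.

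Treatment is open label (6.4). If the test, contrast, time point and components are settled late, they can be settled with outcomes by arm in view, and the reported result may depend on that choice.

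**Working it through.** **1. The plan's own figures (synopsis and 10.6).**
- Sample size: 12 / (1 − 0.20) = 15 per arm, rounded to 16. Total 3 × 16 = 48 = 4 blocks of 12. This reproduces, and it fits a single unstratified list.
- Operating point: effect size 0.9, two-sided 0.05, power 80%. I read 0.9 as a standardized mean difference (assumption) and use the normal approximation.
  - One arm vs one arm: Φ(0.9 × √(16/2) − 1.96) = Φ(0.586) = 72%.
  - Both everolimus arms pooled vs control: Φ(0.9 / √(1/32 + 1/16) − 1.96) = Φ(0.979) = 84%.
- The power claim therefore depends on a contrast that 10.4.2 does not settle.

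**2. One table, two tests.** Take failures of 2/16 and 8/16.
- ANOVA on 0/1 data, without strata. Between-group SS = (0.500 − 0.125)² × (16 × 16/32) = 1.125. Within-group SS = 16 × 0.125 × 0.875 + 16 × 0.5 × 0.5 = 5.75 on 30 df. F = 1.125 / (5.75/30) = 5.87, p = 0.022.
- Fisher, with 10 failures among 32. One tail = [C(16,0)C(16,10) + C(16,1)C(16,9) + C(16,2)C(16,8)] / C(32,10) = 1,735,448 / 64,512,240 = 0.0269. Doubled by symmetry, p = 0.054.

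**3. All tables.** Over the 17 × 17 = 289 pairs of failure counts, the two tests disagree at 0.05 in 22 (11 unordered pairs). ANOVA is the significant one every time. Weighting by binomial probabilities gives the table below. The documents state no event rates, so all rates are assumptions.

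| True rates | Tests disagree | ANOVA significant | Fisher significant |
|---|---|---|---|
| 20% vs 20% | 2.7% | 4.5% | 1.8% |
| 30% vs 30% | 2.4% | 4.3% | 1.8% |
| 40% vs 40% | 2.8% | 4.7% | 1.9% |
| 20% vs 40% | 8.6% | 21% | 13% |
| 20% vs 60% | 14.7% | 65% | 50% |

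**4. If both everolimus arms are tested against control.** This is the exact familywise error of two unadjusted Fisher tests sharing one control arm, with equal rates in all arms and control listed last.
- 16/16/16: 3.4–3.8% at rates of 20–50%, with a maximum of 3.8% over rates of 1–99%.
- 17/17/16: 5.4–6.5% at rates of 20–50%.
- 16/16/15: 5.0–5.5% at rates of 20–50%.

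The unequal sizes are realistic. Sections 4 and 5 plan about fifty patients, which is 4 blocks of 12 plus 2. The Full Analysis Set in 10.1 also drops undosed patients.

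**The case against.** **It is a pilot, and ANOVA on 0/1 data is not badly behaved.** This stands. A reader might infer that ANOVA inflates the false-positive rate. Step 3 shows 4.3–4.7% for a single contrast, so it does not. Nor does a 48-patient pilot make a confirmatory claim.

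**Month 24 is already given.** This stands in part. Two statements of the objective give it, and the mentions of Months 6 and 12 can be read as assessment times. The time point is stated inconsistently; it is not absent. None of the figures above measures the effect of choosing among time points.

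**The randomization list may be stratified.** This cannot be ruled out: 6.5.2 refers to a confidential list that we cannot see. A reader might infer that randomization was certainly unstratified. The documents show only that no factor is described, and the four complete blocks are suggestive, not proof.

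**The choices could multiply to about 10% false positives.** A reader might count six Month 24 readings and reach that figure. It needs a pooled-everolimus contrast that no section specifies, and a choice made after seeing the data. It is an upper bound and is not relied on here.

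**Two Fisher tests are conservative enough to need no adjustment.** That is true at exactly 16 per arm, but not at 17/17/16 or 16/16/15.

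**The supportive analyses are extra tests too.** Those in 10.4.4 are labelled supportive and do not conflict with 10.4.2. The Fisher conflict comes from the synopsis and 10.7.

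**Conclusion.** The point holds. Section 10.4.2 cannot be executed as written, and it conflicts with the synopsis and 10.7 on the test. The contrast, time point and components are each stated inconsistently across the objectives and section 10.

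The size is modest. Choosing between the two tests changes significance in 2.4–2.8% of trials at equal rates of 20–40%, in 8.6% at 20% vs 40%, and in 14.7% at 20% vs 60%. These figures assume 16 per arm, one two-group contrast, no strata in the ANOVA, and event rates that the documents do not supply. The effect of including or excluding delayed graft function is not quantified.

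The harm is a headline result open to selection in an open-label pilot. It should be fixed, because the remedy is cheap and the result otherwise cannot be reproduced from the plan.

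**What to change.** Before any outcome analysis, replace 10.4.2 with one primary analysis, for example:

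> *Primary analysis: composite efficacy failure by Month 24 (components listed here), Full Analysis Set as randomized, [named everolimus arm] vs the MMF/MPA arm, two-sided Fisher's exact test, with a 95% confidence interval for the risk difference. Months 6 and 12 are supportive.*

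With it:
- **Components.** List them once, and make the synopsis (objectives and efficacy assessments), the objectives under section 1, 3.1, 10.4.1 and 10.4.4 identical, including whether delayed graft function counts.
- **Contrast.** Name one as primary (for example Arm 1 vs Arm 3, as 3.1 reads) with the other everolimus arm secondary. If both are primary, use Holm or report the familywise error at the actual arm sizes.
- **Strata.** Delete the ANOVA and the strata sentence. If the list was in fact stratified, name the factor in 6.3 and 10.6 and use a Cochran-Mantel-Haenszel test. State whether it is exact or continuity-corrected, and check its error rate. In a simulation with two assumed strata of 8 per arm and equal rates of 20–50%, two unadjusted contrasts gave a familywise error of about 8–9% uncorrected and 2–4% with the correction.
- **10.4.4.** Correct the reference to two groups.
- **Interpretation.** State that a non-significant result is not evidence of non-inferiority, since section 4 labels the study non-inferiority.

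**Cost.** Wording, by written amendment with IRB approval (12.1), and power: Fisher has about 50% against 65% for ANOVA at an assumed 20% vs 60%, and 13% against 21% at 20% vs 40%. Testing at 0.025, as a Bonferroni adjustment or the first Holm step would, lowers Fisher for a given contrast to about 40% and 9%. That favours naming a single primary contrast.
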